### **F. Data Analysis Plan:**

**Quantitative Statistical Analysis and Power Analysis:** For Aim #2.1, our primary outcome variable will be the post-pre change in CD-RISC scores in intervention and control subjects. Previous studies suggest that clinically significant changes in CD-RISC scores range from 12-19 points with an approximate standard deviation of 20 points. With a total enrollment of 160 subjects, we will be able to detect a difference of 12 points in CD-RISC score between the control and intervention groups with 90% power (assuming a 2-sided significance level (alpha) of 0.05 and an equal variance *t* test; software: PASS 13); we will be able to detect a difference of 19 points in CD-RISC score between the control and intervention groups with 100% power. We will also examine the change in MBI, PDS, and HADS scores in both the treatment and control groups. We will corroborate our comparisons of changes in all scores using robust bootstrap and permutation methods. When measuring constructs involving psychological mood, there is always concern that the answers reflect transient, less stable responses. The participant responses may simply change over time making certain paired analyses difficult to interpret. Therefore, we will calculate a coefficient alpha to estimate measurement reliability.

If we fail to find a bigger increase in CD-RISC score in the intervention group, as we expect, that may be due to interactions (contamination) between members of the intervention and control groups. We will assess the extent of contamination in Aim #2.2, for which our primary outcome variable will be the change in mean baseline CD-RISC score over time within each ICU. If there is, on average, greater than 30% contamination (that is, if baseline pre-enrollment CD-RISC scores increase), we will consider using a randomized cluster design for the subsequent multi-center clinical trial. If baseline CD-RISC scores increase 4 points over each intervention period, we will be able to detect that progressive increase with roughly 92% power (10,000 simulations using the Jonckheere-Terpstra ordered alternatives procedure; software: R). Our assessment of changes in baseline CD-RISC scores over time will consider the point and interval estimates of the changes in addition to formal statistical significance which may be of less use in this setting. All analyses will use SAS 9.3 and  $p < 0.05$  will be considered significant.

**Qualitative Statistical Analysis:** Analysis of qualitative data is planned as a continuous process beginning with initial interviews and continuing throughout and beyond the data generation period. Analysis of the transcripts will begin with repeated readings to achieve immersion, followed by coding using an emergent rather than a priori approach, in order to emphasize focus group perspectives and de-emphasize specific speculations. The synthesis stage of data analysis involves triangulating the findings from focus groups, as well as individual demographics. The trustworthiness of study results will be enhanced through attention to data credibility, transferability, dependability, and confirmability. The software package ATLAS.ti v 7.0 will be used to manage and analyze the qualitative data. Consistent with the NIH guidance on mixed methods research, we will integrate the findings from the quantitative surveys with the qualitative findings.

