#### IV. Research Methods

**Recruitment and Informed Consent Process:** When a nurse hears about the study and they are interested in participating, they will contact the study team by phone or email. They may also be contacted while study staff are recruiting in-person.

- Next, the nurse will complete the pre-consent, screening survey: the Connor-Davidson Resilience Scale (CD-RISC), Maslach Burnout Inventory (MBI) and demographic questions. This will happen one of two ways: 1) in-person hard copy form, OR 2) survey link sent through email.
- If the participant scores:
  - *< 82 on the Connor-Davidson Resilience Scale (CD-RISC) indicating decreased resiliency; AND, positive scores in at least one BOS dimension using the Maslach Burnout Inventory (MBI): emotional exhaustion score of >17, depersonalization score of >7, or a personal accomplishment score of < 31; AND,*
  - *They work at least 20 hours per week in an ICU; AND,*
  - *They do not have a known diagnosis of bipolar disorder, psychotic disorder, or an active substance dependence,*
  - they have passed the first eligibility screen for the study and will either receive a REDCap prompt to complete the electronic informed consent OR will complete the informed consent after having all their questions addressed by study staff. If they do not receive these scores, they will be automatically notified by RECap that they do not qualify for the study OR the study staff will score the hard-copy tools and will notify them in-person.
- **Electronic Consent:** If a nurse completes the REDCap pre-consent survey link and they are eligible to participate, they will be prompted to read and sign an electronic consent. There will be a statement notifying them to contact a member of the study team if they have questions, or need more information before signing the consent. Nurses will confirm that they have read the consent language, understand the risks and benefits of the study, understand their involvement in the study and are prepared to consent to the study. They will then give their informed consent electronically. Study staff will have in-person, email or phone contact with the nurse before the consent is signed, so the study staff can affirm that the nurse is prepared to provide informed consent.

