**Methods/Randomization:** At study entry all participants will complete the Hospital Anxiety and Depression Scale (HADS). The HADS is a 14-item screening scale developed to indicate the possible presence of anxiety and depression . HADS consists of a 7-item anxiety subscale and a 7-item depression subscale. A score of > 8 identifies a positive history of anxiety or

depression symptoms . The validity of the HADS has been extensively studied in a variety of populations including the general population, general practice and psychiatric patients. In our previous analyses of ICU nurses, the HADS Cronbach's alpha was 0.86 3, 8. In order to complete Aim 2.2 and due to our staffing capacity, we will conduct one treatment and one control group in each 16 hour intervention period. We will recruit ~24 nurses at a time, who will be randomized on a 1:1 basis to either treatment (n=12) or control (n=12). Therefore at least 10 months will be required to complete the pilot study (5 treatment and 5 control cohorts x 2 month interventions = 10 months).

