#### **A. Outcome Measure(s):**

##### **Outcomes Variables:**

1. **The primary outcome** will be post-pre changes in the CD-RISC scores in intervention and control subjects.
2. **Acceptability** will be measured with the eight-item self-report Client Satisfaction Questionnaire (CSQ-8) 103, 138. The CSQ-8 is designed to yield a homogeneous estimate of general satisfaction. Scores range from 8 to 32 (higher scores indicating greater satisfaction). The CSQ-8 will be administered after the final treatment and control session.
3. **Adherence** will be measured for each component of the intervention and a total overall adherence will be calculated. Our research personnel will record study participant's attendance at each of the sessions and completion of assigned daily practices. Study participants will complete REDCap diary cards and record their weekly participation in out of class activities. Adherence will be calculated from these two sources of information. The total adherence will be calculated by adding each individual intervention component adherence divided by the total number of components.
4. **Additional outcomes:** Participants will also complete post-intervention MBI, PDS, and HADS surveys.
5. **Qualitative Interviews** will also be administered to provide an assessment of participant satisfaction with the intervention and control program. Interviews will be digitally audio recorded and transcribed for coding. Three questions specifically inquired about the helpfulness of the intervention and control programs: "Has the program been helpful to you?" "Has the program changed how you cope with work related stress?" and "Has the program changed how you cope with times when you feel you may start to become stressed at work?" Additional open-ended questions will be used to elicit participant descriptions of their program experience. These interviews will be audio recorded and transcribed as described in Aim 1.

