##### **Inclusion Criteria:**

1. Male or female, ages 18+
2. Employed as a critical care nurse and work at least 20 hours per week as an ICU.
3. Baseline score of < 82 on the Connor-Davidson Resilience Scale (CD-RISC)

4. Positive symptoms of at least one BOS dimension using the Maslach Burnout Inventory (MBI): emotional exhaustion score of >17, depersonalization score of >7, or a personal accomplishment score of < 31

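### The primary CD-RISC comparison names no baseline covariate; adjusting for screening CD-RISC would tighten the estimate modestly at almost no cost

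*Combined protocol and SAP*

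**What the plan says.** Outcomes Variables (section A) gives the primary outcome as "post-pre changes in the CD-RISC scores in intervention and control subjects", and the Data Analysis Plan (section F) repeats this for Aim 2.1: "our primary outcome variable will be the post-pre change in CD-RISC scores in intervention and control subjects". No analysis model is written out. The nearest thing is the power statement, which works by "assuming a 2-sided significance level (alpha) of 0.05 and an equal variance" t test. The supporting analyses stay on the same scale: "We will corroborate our comparisons of changes in all scores using robust bootstrap and permutation methods". No section names a covariate or an adjusted model.

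Baseline values are already collected. Under Recruitment and Informed Consent in section IV, "the nurse will complete the pre-consent, screening survey: the Connor-Davidson Resilience Scale (CD-RISC), Maslach Burnout Inventory (MBI) and demographic questions". The CD-RISC score must be below 82 for a nurse to be eligible, so every randomized nurse has one. HADS is taken at study entry (Methods/Randomization).

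**The concern.** A change score subtracts the whole of the baseline, which fixes its coefficient at 1. Adjustment estimates that coefficient. When the true slope of post on pre is below 1, full subtraction adds noise. The plan gives a reason to expect this: section F worries that mood-related answers may be transient and may make paired analyses hard to interpret. The reliability coefficient it offers in response does not change the estimator.

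The stake is precision, not validity. Both estimators are unbiased under 1:1 randomization, and regression to the mean after selection below 82 affects both arms alike. The estimate is meant as preliminary data for a larger trial (section G), so the width of its interval matters as well as its p-value.

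**Working it through.** **Inputs from the documents**
- 160 nurses in total, so 80 per arm; a 12-point difference; SD 20; two-sided alpha 0.05 (section F).
- 5 periods × 24 nurses = 120, so 60 per arm (Methods/Randomization).
- Eligibility cut-off below 82 (Inclusion Criteria).
- 22% of surveyed ICU nurses at CD-RISC 92 or above (Preliminary Studies, item 6).

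**Assumptions**
- Source scores are normal.
- The slope *b* of post on pre is between 0.4 and 0.7, with values up to 0.9 also shown. The documents give no correlation.
- The plan says that "clinically significant changes in CD-RISC scores range from 12-19 points with an approximate standard deviation of 20 points". It does not say whether 20 is the SD of a single score or of the change, so both readings are tried.

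**Step 1: the plan's power figure.** At 80 per arm the SE is 20 × √(2/80) = 3.16. The t test then has 96.5% power for 12 points, not the stated 90%. At 60 per arm power is 90.3%, which matches. The stated 100% for 19 points reproduces. The mismatch between 160 and 90% is a separate matter that adjustment does not settle, so both sample sizes are carried below.

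**Step 2: baseline spread after the cut-off** (20 read as the SD of a single score). Source mean = 92 − 0.772 × 20 = 76.6. Truncating this normal distribution at 82 leaves 0.427 of the variance: 0.427 × 400 = 170.8, so the baseline SD is 13.07.

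**Step 3: variance per nurse**
- Adjusted: 400(1 − b²)
- Raw change: 400(1 − b²) + (1 − b)² × 170.8

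| b | Adjusted | Raw change | Variance reduction | Interval narrower by |
|---|---|---|---|---|
| 0.4 | 336.0 | 397.5 | 15.5% | 8.1% |
| 0.5 | 300.0 | 342.7 | 12.5% | 6.4% |
| 0.6 | 256.0 | 283.3 | 9.6% | 4.9% |
| 0.7 | 204.0 | 219.4 | 7.0% | 3.6% |
| 0.8 | 144.0 | 150.8 | 4.5% | 2.3% |
| 0.9 | 76.0 | 77.7 | 2.2% | 1.1% |

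**Step 4: 95% half-widths** = t × √(2 × variance / n per arm)
- 80 per arm: 6.23 falls to 5.72 points (b = 0.4); 4.63 falls to 4.46 (b = 0.7).
- 60 per arm: 7.21 falls to 6.63 (b = 0.4); 5.35 falls to 5.16 (b = 0.7).

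In nurses, 160/(1 − 0.155) − 160 = 29 and 160/(1 − 0.070) − 160 = 12. The gain at 160 is therefore worth 12 to 29 extra participants.

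**Step 5: other readings of the SD**
- If 20 is the SD of the change (variance 400) and the baseline SD stays at 13.07, the reduction is (1 − b)² × 170.8/400, or 15.4% at b = 0.4 and 3.8% at b = 0.7.
- With a source SD of 15, the source mean is 80.4, the truncated SD is 9.33, and the reduction is 14.2% to 6.4%.

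**Step 6: cost of estimating the slope.** The critical t moves from 1.9751 to 1.9752 and the variance inflates by about 1/156 = 0.6%. A simulation of 20,000 trials with a true effect of 12 points gave a mean estimate of 12.0 for both methods. The variance reductions at 80 per arm were 14.7% (b = 0.4) and 7.1% (b = 0.7). At 60 per arm they were 14.4% and 5.5%.

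**Step 7: what this means in one trial.** A chance baseline difference of *d* points between arms moves the raw-change estimate by (1 − b)d. The SE of the baseline difference is 13.07 × √(2/80) = 2.07, or 2.39 at 60 per arm. A difference of 3 points or more, in either direction, then has probability 15% or 21%. It moves the estimate by 1.8 points (b = 0.4) to 0.9 (b = 0.7). With a source SD of 15 the probabilities are about 4% and 8%.

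**The case against.** The strongest reply is that this is a choice between two valid estimators and that no decision in the pilot turns on it. Reading 20 as the SD of change, power for 12 points is already 90.3% at 120 nurses and 96.5% at 160. The half-width at 80 per arm falls by only 0.51 points (b = 0.4) or 0.17 points (b = 0.7). Aims 2a and 2b concern acceptability and the level of randomization, and neither depends on this gain. All of that stands. It limits the importance of the point but gives no reason to prefer the less precise estimate.

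Three objections to the size are also fair:
- Slopes above 0.7 are possible, and the gain then falls to 4.5% or 2.2% of the variance, less the 0.6% inflation.
- Both arms are delivered in groups of about 12, and an individual baseline covariate does not remove variation that arises within the groups after randomization. With an assumed intraclass correlation of 0.05 in both arms, the design effect is 1 + 11 × 0.05 = 1.55. The reductions shrink to 15.5%/1.55 = 10% and 7.0%/1.55 = 4.5%, and all the half-widths above would be too narrow.
- The shift from chance imbalance is not a second harm. Its variance is the (1 − b)² × 170.8 term already counted in Step 3.

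None of these reverses the direction or adds a real cost.

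**Conclusion.** The concern holds as a modest refinement. The plan names no baseline covariate for its primary comparison, and the obvious one is measured on every nurse before randomization. Under the stated assumptions and independence between nurses, adjustment lowers the variance by about 15% to 7% for slopes of 0.4 to 0.7, and by 2% at 0.9. Allowing for grouping at an assumed intraclass correlation of 0.05 gives about 10% to 4.5% for slopes of 0.4 to 0.7. The omission and the direction of the gain are certain. The size is not, because the documents give no pre-post correlation. The unadjusted comparison remains valid, and adjustment settles neither the sample-size mismatch nor the group delivery.

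**What to change.** In section F, state that the primary estimate is the between-arm difference from a linear model of post-programme CD-RISC on arm, with screening CD-RISC as covariate. Using the change as the response gives the same arm effect. Apply the bootstrap and permutation checks to this adjusted estimate. Treat MBI and HADS in the same way with their own baselines; PDS can follow once the plan says when its baseline is taken. Keep the change-score t test as a sensitivity analysis, which also preserves the link to the power statement.

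Fix the covariate before any outcome data are seen, so that it cannot be chosen by its effect on the result. The cost is a sentence or two in the analysis plan and one degree of freedom per model, with no new data. The same model can later take a term for treatment group if the sponsor decides to address group delivery.

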care, lower patient satisfaction, increased number of medical errors, increased rates of health-care associated infections, and higher 30-day mortality rates 19, 20. In addition, BOS contributes to our growing nursing shortage that is shortly expected to exceed 1,000,000 positions (29% vacancy rate) 21, 22. The national nursing shortage is even more of a problem in specialty areas such as the ICU 23. One reason for the shortage is that nurses are leaving their profession at an alarming rate. In a national survey, 41% of nurses were not satisfied with their job and 22% planned on leaving their profession. When asked why they were considering leaving the nursing profession, 56% desired a less stressful position 24. In the ICU, annual national nursing turnover rates exceed 17-20% 25, 26. Our recent survey confirmed these findings and also identified annual ICU nursing turnover rates as high as 40% (unpublished data). Independent of BOS, ICU nursing turnover is also associated with increased healthcare costs, decreased nursing productivity, reduced the quality of nursing care, and diminished staff morale 26, 27, 28. National surveys reveal that replacing one critical care nurse costs more than \$65,000 29. Therefore, at a medium sized hospital with 40 ICU beds, the cost of ICU nursing turnover is over \$1,000,000 per year. As a result, hospital administrators have prioritized implementing methods to reduce ICU nursing turnover rates 30.

**Several studies have tried to identify methods to reduce BOS in a variety of high stress occupations.** These studies have examined many interventions including: relaxation therapy, laughter therapy, counseling and psychosynthesis. However, the majority of these studies were hampered by several important limitations.

1. Most studies were performed in a non-randomized manner and did not include a control group.
2. Usually, those studies with a control arm used a passive control arm. Passive control arms cannot account for the important impact of simply delivering additional support and attention to the treatment group.
3. In those studies of healthcare professionals, the most common outcome was simply the change in BOS symptoms. Clinically relevant outcomes such as quality of care or turnover rates have not been examined.

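### The primary CD-RISC analysis names no analysis set and no method for a missing post score, so it defaults to nurses with both surveys and leaves the baseline scores unused as covariates

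*Combined protocol and SAP*

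**What the plan says.** The outcomes list in section A says the primary outcome "will be post-pre changes in the CD-RISC scores in intervention and control subjects". Section F repeats it: "our primary outcome variable will be the post-pre change in CD-RISC scores in intervention and control subjects". The only test named is an equal-variance t test, and it appears inside the power assumption: "we will be able to detect a difference of 12 points in CD-RISC score between the control and intervention groups with 90% power", with 160 enrolled, an "approximate standard deviation of 20 points" and "assuming a 2-sided significance level (alpha) of 0.05". The robustness check is "We will corroborate our comparisons of changes in all scores using robust bootstrap and permutation methods".

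The document does not state an analysis population, an as-randomised rule, an imputation or likelihood method for a missing post score, an expected loss rate, a comparison of loss between arms, or a missing-data sensitivity analysis. It also does not say in words that nurses without a post survey are left out.

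CD-RISC, MBI and demographics are collected at screening, and HADS at study entry (section IV). Section F gives none of them a role as a covariate or in handling missing scores.

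**The concern.** A change score needs both surveys. With no other method given, the comparison falls back on nurses who returned the post survey. Bootstrap and permutation on the same observed changes reuse the same nurses, so they cannot show whether those nurses are a selected group.

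Several features make outcome-related loss plausible:

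- Entry requires low resilience and at least one positive burnout dimension.
- The background section links burnout to turnover and says that in the ICU "annual national nursing turnover rates exceed 17-20" percent, with rates up to 40% in the team's own survey.
- In the preliminary exit interviews, 3 of 4 departing ICU nurses gave stress or burnout as the main reason, although four is a very small sample.
- The arms differ in demand: 16 hours of MBCT-ICU with daily meditation and homework, against a book club with daily reading.
- The suicidality response plan withdraws some participants, and nothing says how their outcome is treated.

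The arm difference is meant to serve as preliminary data for a larger trial (section G), so a distortion in it would carry forward. Leaving the baseline scores out also gives up precision that is already paid for.

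**Working it through.** **1. The plan's own power figure.** Inputs from section F: difference 12, SD 20, two-sided alpha 0.05, equal-variance t test, 1:1 allocation. Noncentrality = 12 / (20 × √(2/n)).

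- n = 80 per arm (160 analysed): 12/3.16 = 3.79, exact power 96.5%.
- n = 60 per arm (120 analysed): 12/3.65 = 3.29, exact power 90.3%.

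The stated 90% therefore matches 120 analysed, not 160. The figure for 19 points ("we will be able to detect a difference of 19 points in CD-RISC score between the control and intervention groups with 100% power") reproduces. The number 120 equals five rounds of 24 nurses (Methods/Randomization), and also 160 × (1 - 0.25). The text does not say which was meant, so no loss allowance can be read from it. The simulations below use 60 per arm unless stated.

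**2. Loss implied by turnover.** Over a two-month round, 1 - (1 - y)^(2/12) for annual turnover y gives 3.1% (17%), 3.7% (20%) and 8.2% (40%). Any loss beyond that is an assumption.

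**3. When a completers-only difference is biased.** Bias = loss_T × gap_T - loss_C × gap_C, where T is MBCT-ICU, C is the book club, and gap is mean change in completers minus mean change in those lost.

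- Gap 0 in both arms: bias 0, however uneven the loss.
- Loss 30% vs 10%, gap 12 in both arms: 3.6 - 1.2 = 2.4 points.
- Loss 20% in both arms, gap 12 in one arm only: 2.4 points.

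So uneven loss is neither sufficient nor necessary. What matters is whether loss is related to change, and whether its amount or reasons differ by arm.

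**4. Effect of the entry cap.** Assume a normal source population with SD 20 in which 22% score 92 or more (the national survey in section III). The mean is 92 - 0.772 × 20 = 76.6. Restricting to CD-RISC below 82 gives a baseline SD of about 13.

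**5. Loss driven by low baseline CD-RISC.** Simulated with no true effect, pre-post slope 0.5 and logistic loss of 10% vs 5%, 20% vs 5% and 30% vs 10% (MBCT-ICU vs control). All of these are assumptions.

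| Setting | Change-score bias (points) | Type I error |
|---|---|---|
| No cap, stronger selection | about -0.5, -1.6, -2.1 | up to about 8% |
| With cap, stronger selection | about -0.35, -0.9, -1.1 | 4.8-6.2% |
| With cap, weaker selection | -0.2 to -0.8 | about 5% |

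The sign is negative because low scorers tend to rise on retest, and more of them are lost from MBCT-ICU. Adjustment for baseline CD-RISC brought the bias to about 0.2 points or less.

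**6. Loss driven by a low post score.** Simulated with baseline SD 20 and no cap: change-score bias +0.3 to +2.2 points, baseline-adjusted bias +0.5 to +3.3. Adjustment is worse here.

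**7. Loss driven by another baseline covariate.** Change-score bias was at most 0.2. Adjusting for CD-RISC alone left up to +0.9, and adding that covariate brought it to about 0. This is why the missing-data model needs MBI, HADS and demographics as well.

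**8. Precision.** With slope 0.5 and SD 20, residual variance is 400 - 0.25 × 400 = 300 (SD 17.3).

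- No cap: change-score SD is √(0.25 × 400 + 300) = 20; 17.3/20 = 0.87, a cut of about 13%.
- With cap: √(0.25 × 169 + 300) = 18.5; 17.3/18.5 = 0.94, a cut of about 6%.

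Simulation gives about 12% without the cap and 5-6% with it.

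**The case against.** - **Exclusion is not a stated rule.** A reader might infer that the plan removes every nurse without a post survey. The document does not say so: it defines an outcome, and an analyst could impute a change score. This stands. What can be said is that completers are the default when nothing else is specified.
- **Uneven loss alone does not bias the difference.** This stands (step 3).
- **The evidence for heavy or uneven loss is thin.** Turnover applies to both arms. A nurse who leaves the job can still answer an emailed survey. The earlier pilot reports 27 nurses who took part and completed, with full attendance at the workshop and CBT sessions, though it does not report how many were randomised. Nurses unwilling to follow the whole protocol are excluded, and the control is active. This largely stands: losses of 20% or 30% have no source in the document.
- **A reader might infer that false claims of benefit become more likely.** When loss follows low baseline, the bias runs against MBCT-ICU; with the cap, false positives in its favour were about 1.2-2.4%, below the nominal 2.5%. Error inflated in its favour needs loss tied to the post score, which the document neither shows nor rules out.
- **Adjustment is not uniformly better, and this is a pilot.** Both are true. Step 6 shows a case where adjustment is worse, and that must be disclosed. The remedy should stay proportionate to an R34 pilot.

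**Conclusion.** The gap is real and moderate in consequence. The plan leaves the analysis set and the handling of missing post scores unstated, so the primary comparison defaults to nurses with both surveys and makes no use of baseline data as covariates.

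At the assumed losses, with loss following low baseline CD-RISC and the entry cap applied, the bias is about -0.2 to -1.1 points. The upper end is 1.1/12, or about 9% of the target difference, and type I error stays near 5-6%. Loss following the post score could give larger bias of the opposite sign, and no baseline model removes it. These sizes rest on assumed loss rates, a slope of 0.5 and a normal source population; only the turnover arithmetic comes from the document.

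The document does not support saying that the arm difference will be biased, or that a 25% loss was planned. The case for change rests as much on the precision gain of roughly 5-13% and on fixing the method in advance as on the likely bias.

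**What to change.** In section F:

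1. Name all randomised nurses, analysed as randomised, as the primary analysis set.
2. Make the primary estimate the arm difference in post CD-RISC adjusted for baseline CD-RISC. Handle missing post scores under missing at random, by multiple imputation within arm from baseline CD-RISC, MBI, HADS and demographics, or by an equivalent mixed model.
3. Keep the change-score t test, with its bootstrap and permutation checks, as a sensitivity analysis.
4. Add one simple delta-adjusted run, lowering imputed MBCT-ICU scores by, for example, 4, 8 and 12 points.
5. Report loss and its reasons by arm.

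In section A, state that the post REDCap survey goes to every randomised nurse at the end of the round, whether or not still attending. Also state whether 160 or 120 is the number to be analysed, and what loss allowance, if any, is included.

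The cost is plan wording and a little programming; the surveys already run in REDCap. State the downsides in the plan: the main analysis relies on missing at random, the estimate may be slightly less favourable, and if loss depends on the unseen post score the adjusted estimate can be somewhat more biased than the change score.

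### The power statement assumes 160 nurses, but the listed cohorts add up to about 120, and the stated 90% power fits 120 rather than 160

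*Combined protocol and SAP*

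**What the plan says.** Section F (Data Analysis Plan) makes the primary-outcome power claim: "With a total enrollment of 160 subjects, we will be able to detect a difference of 12 points in CD-RISC score". It puts the power for that difference between the arms at 90%. The claim assumes a two-sided alpha of 0.05, an equal-variance t test and an SD of about 20 points. The 12 points are the lower end of the range the plan treats as meaningful: "clinically significant changes in CD-RISC scores range from 12-19 points". The same sentence claims 100% power at 19 points.

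Section IV (Research Methods, Methods/Randomization) sets the enrollment schedule. About 24 nurses are recruited at a time and "randomized on a 1:1 basis to either treatment (n=12) or control (n=12" per group. One group per arm runs in each period: "due to our staffing capacity, we will conduct one treatment and one control group in each 16 hour intervention period". The stated duration is at least 10 months, worked out as "5 treatment and 5 control cohorts x 2 month interventions = 10 months".

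Section A (Outcome Measures) makes CD-RISC change the primary outcome: it "will be post-pre changes in the CD-RISC scores in intervention and control subjects".

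For Aim 2.2, section F adds a simulated power for a 4-point rise in baseline CD-RISC per intervention period: "we will be able to detect that progressive increase with roughly 92% power". It names the Jonckheere-Terpstra procedure and 10,000 simulations, but not the number of rounds, nurses per round, SD or sidedness.

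**The concern.** The two sections describe different trial sizes. The listed cohorts fall 40 nurses short of the enrollment on which the power is stated, and nothing in the documents explains the gap. The stated power also looks as if it was calculated for the smaller total.

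This bears on the formally powered comparison of the named primary outcome. A reader cannot tell whether the target is 160 with some reserve, or 120 with none. The same ambiguity affects the planned duration and any later judgement of whether recruitment met its target.

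**Working it through.** **Enrollment implied by the schedule** (section IV)

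- Per round: 12 treatment + 12 control = 24.
- Rounds: 5 treatment and 5 control cohorts, one of each per period = 5 rounds.
- Total: 5 × 24 = about 120. Gap to section F: 160 − 120 = 40.
- Rounds of 24 needed for 160: 160 / 24 = 6.7, so seven rounds (six of 24 and one of 16). At 2 months each, that is 14 months.

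**Primary-outcome power** (section F inputs: difference 12, SD 20, two-sided alpha 0.05, equal-variance t test; section IV: 1:1 allocation)

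With n per arm, the noncentrality is λ = 12 / (20 × √(2/n)) on 2n − 2 degrees of freedom. Power is the probability that a noncentral t variable with that λ lies beyond the two-sided 5% critical value.

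| Total | n per arm | λ | Critical t | Power |
|---|---|---|---|---|
| 160 | 80 | 3.79 | 1.975 | 96.5% |
| 120 | 60 | 3.29 | 1.980 | 90.3% |
| 118 | 59 | 3.26 | 1.981 | 89.8% |

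The plan's 90% is not reproduced at 160. It is reproduced at 120, which is also the smallest balanced total that reaches 90%. The difference detectable with 90% power is 10.3 points at 160 and 11.9 points at 120.

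The second claim does not separate the two totals: at 19 points, power is 99.997% with 160 and 99.93% with 120, and both round to 100%.

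**Effect of losses.** The documents state no attrition rate, so these rates are assumptions.

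| Assumed loss | Evaluable per arm, 160 enrolled | Power | Evaluable per arm, 120 enrolled | Power |
|---|---|---|---|---|
| 10% | 72 | 94.7% | 54 | 87.1% |
| 15% | 68 | 93.5% | 51 | 85.1% |
| 20% | 64 | 92.0% | 48 | 82.9% |

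**Could 160 give 90% on some other basis?** Each of these would bring it to about 90%, and none is stated:

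- 25% loss: 160 × 0.75 = 120 evaluable, power 90.3%.
- Clustering within groups of 12 with an intraclass correlation of 0.03: design effect 1 + 11 × 0.03 = 1.33, effective total 160 / 1.33 = 120.3, power 90.4%.
- An SD of 23.3, where section F gives about 20.
- 3:1 allocation, power 90.4%, which contradicts the stated 1:1.

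**The case against.** **An allowance may lie behind 160.** It could be 120 inflated for 25% loss, since 120 / 0.75 = 160. That is plausible, but no section says so, and section F attaches the power to total enrollment. It would also leave the schedule unchanged, with rounds that enroll about 120.

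**The schedule is approximate.** Section IV recruits roughly 24 at a time and gives its duration as a minimum. This stands in part: the text does not rule out further rounds, so the accurate statement is that the listed rounds do not add up to 160. The explicit count of five cohorts per arm still does not stretch to 160.

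**The consequence is modest.** If 160 are enrolled, power is understated and nothing is lost; even an assumed 20% loss leaves 92%. At 120, a very small loss hardly matters: 59 per arm gives 89.8%. The trial is also a pilot meant to inform a larger one. All of this stands, and it limits the severity. It does not remove the contradiction, because the plan makes a formal power claim for its primary outcome.

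**A stronger reading of Aim 2.2 is not supported.** A reader might infer that the roughly 92% power is also wrong, or that it could mislead the choice of a cluster design for the next trial. The documents do not give the simulation's rounds, SD, sidedness or handling of ICUs. They also do not say whether it covers all screened nurses or only those enrolled, whose scores are limited by the CD-RISC entry cut-off of below 82. Without these, the figure cannot be confirmed or refuted. Section F ties the design choice to observed contamination and to point and interval estimates, not to the planning power.

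**Conclusion.** The contradiction is real and the plan is wrong as written: section F's 160 and section IV's roughly 120 cannot both be the enrollment. Under section F's own assumptions, the stated 90% belongs to 120 (90.3%) and is 6.5 percentage points too low for 160 (96.5%).

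These figures assume SD 20 for the change score, 1:1 allocation, complete follow-up and independent observations. If 160 are enrolled, the error is conservative. If only the five listed rounds are run, the claim has no reserve, and assumed losses of 10% to 20% bring power to about 87% to 83%.

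This should be fixed but does not invalidate the trial. A reader might infer that the primary comparison is underpowered; the documents do not establish that, because they do not settle which total will be enrolled or what loss is expected. For Aim 2.2, the finding is only that the simulation's inputs are unreported.

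**What to change.** State one enrollment in sections IV and F, with matching rounds, duration and power. Two routes are open.

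- **Keep 160.** Either state its basis (for example an attrition allowance, with its value) or restate the power as about 96.5% with complete follow-up and independent observations. Revise section IV so that its rounds deliver 160 within the stated staffing capacity: about seven rounds of 24, or 14 months.
- **Adopt 120.** Replace 160 in section F, keep five rounds, say that 90% assumes complete follow-up, and give the power at the expected loss.

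In either case, confirm that the Aim 2.2 simulation was run for the chosen rounds, rerun it if not, and state its number of rounds, nurses per round, analysis set, SD, sidedness and handling of ICUs.

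The cost is restated figures in two sections and at most one simulation rerun. Keeping 160 adds about 4 months to the listed 10 but no nurses beyond those section F already states. Adopting 120 keeps the schedule but leaves essentially no reserve for loss.
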